IRB Study Number: 20161061

Intraoperative Efficacy of Suction Enabled Retraction Device in Lumbar Spine Surgery

National Clinical Trial Number: **NCT03160170**

Study Number: 20161061

Date: March 15, 2017

Principal Investigator: [name]

1) Protocol Title

Intraoperative Efficacy of Suction Enabled Retraction Device in Lumbar Spine Surgery

2) Objectives*

This is a prospective randomized controlled trial of a new surgical instrument to assess:

- Effects on operative time and efficiency of exposure in open lumbar spine cases.
- Effect on total blood loss during the exposure part of the operation.
- Rate of clogging of suction device.

3) Background*

During spinal surgery, exposure of bony anatomy requires the use of retraction, suction, and electrocautery at the same time. As three instruments are generally used – a Cobb elevator, electrocautery, and suction – an assistant is generally required or the primary surgeon has to switch between the instruments. The resultant juggling of instruments and/or reliance on an assistant can influence operating time and efficiency.

The new device, Suction-Integrated Surgical Tissue Elevator & Retractor [SISTER], is shaped like a Cobb elevator but also has a hollow core allowing suction tubing to be connected. Thus, a single hand can be used to retract and suction at the same time while the other hand separates soft tissue from the bones with electrocautery. This set up which is proposed to be more efficient will be evaluated in this study.

The device is made of high density plastic material and is disposable. The device meets FDA's Medical Device Exemption 510(k) Requirements (Please see uploaded letter from Ludwig Medical Corporation).

4) Inclusion and Exclusion Criteria*

Inclusion

English-speaking patients undergoing Lumbar One to Sacral One open instrumentation performed by attending physicians in the Departments of Neurological Surgery and Orthopedic surgery will be included.

Exclusion

- Age less than 22 years old
- Patients whose procedure will not involve instrumentation

- Patients with prior Lumbar spine surgery involving more than one level
- BMI less than 20 or greater than 35
- Patients with known bleeding conditions (ex: Factor V Leiden, Von Willebrand's,)
- Patients that routinely take anticoagulation medicine (ex. Aspirin 325mg/day, Plavix)
- Operative cases where a single surgeon performs both sides of exposure.
- Pregnant women
- Prisoners
- Adults unable to consent

5) Procedures Involved*

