Patients will be selected prospectively and randomly assigned to either the control group (standard exposure technique) or the suction-integrated Cobb group. Randomization will be performed with a coin toss: “best two out of three” style. For example, if “heads” represents the “control” group, 2 out of 3 tosses resulting in “heads” will assign a given patient to the control group, and if “tails” represents the “suction-integrated Cobb group” 2 out of 3 tosses resulting in “tails” will assign the patient to the suction-integrated Cobb group. Randomization will stop once 20 subjects are enrolled in the suction-integrated Cobb group. If at that time, the control group has less than 20 subjects, all subsequent subjects will be assigned to the control group.

During the consent process, patients will be informed that a new instrument may be used during their surgery. The risks of using the device will be explained to the patient, which will include the surgeon’s discomfort when using the new instrument, or failure of the device, which may lead to a delay during the exposure phase of surgery, which could ultimately result in a longer surgery. Surgeons will be given time to become familiar with the instrument. Operative data will be collected.

In the control group, the surgeons will utilize standard exposure technique and instruments. In the suction-integrated Cobb group, surgeons will be provided with the device. Standard equipment will also be readily available in case the surgeon decides for any reason not to use the device. The device will be provided by Ludwig Medical Corporation, the manufacturers of the device.

The following data will be recorded: age, gender, BMI, spinal levels involved, overall operative time, exposure time measured from skin incision until adequate exposure is achieved by the surgeon, blood loss during the exposure, and number of times the suction had to be unclogged.

No postoperative follow up is required.

A total of 40 patients will be randomized, with twenty assigned to each group.

6) Data Management*

All study staff will be CITI certified and will be trained in handling confidential medical information. Data will be stored on a password-protected computer in a secured location. Data will be coded and each subject will be assigned a unique study number. The linking code will be stored separately and will only be accessible to the study team. Only research members approved by the IRB will have access to the data.

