Power analyses has determined that 36 subjects (2 groups of 18) would be sufficient to demonstrate a significant effect. The parameters and assumptions of this analysis are as follows: an average exposure time with typical instruments of 30 (± 15) minutes, a 45% reduction in exposure time previously demonstrated in a previous small study with the new device, a 1:1 enrollment ratio for sub-groups, an alpha value of 0.05 for significance, and power value of 80%. Our proposed study size of 40 subjects will therefore confer statistical power.

7) Provisions to Monitor the Data to Ensure the Safety of Subjects

The PI will be responsible for data and safety monitoring. Any suspected or observed breach in data security will be reported to the PI and IRB.

The data collected and planned analyses are described above. Data will be collected before, during, and after each patient's surgery, and will be reviewed by study staff. The trial will be suspended if a breach of security is observed, or harm is demonstrated to subjects.

8) Withdrawal of Subjects

Subjects will be withdrawn from the study if their planned surgical procedure is cancelled or changed in such a way as to no longer meet inclusion criteria for the study. If a subject withdraws from the study, or is withdrawn from the study, the study staff will stop collecting new information about the subject. However, the study team will use the information they have already collected.

9) Risks to Subjects*

The risks associated with this study are largely those of the surgery itself. Additionally, the surgeon may not be comfortable using the new instrument, or the device may fail, which may lead to a delay during the exposure phase of the surgery. Also, as part of this research, there is a possibility of a breach of confidentiality (your private information) of your medical data. We will take adequate steps to protect your confidentiality. In addition, there may be uncommon or previously unknown risks that might occur.

10) Potential Benefits to Subjects*

Patients may benefit from a potential decrease in operative time, anesthesia time, and reduced blood loss.

11) Vulnerable Populations*

Not applicable.

12) Setting

The research will be conducted at Jackson Memorial Hospital.

13) Resources Available

All research personnel are CITI Certified.

Ludwig Medical Corporation will provide 40 devices free of charge for the study.

14) Recruitment Methods

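### The clogging count can miss the clog that ends use of the device, and it mixes device clogs with clogs of the fallback suction

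*Combined protocol and SAP*

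**What the plan says.** The third objective in Section 2 is "Rate of clogging of suction device". It gives no definition, denominator or time window.

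The data list in Section 5 has one clogging item, the "number of times the suction had to be unclogged". It has no item for setting the device aside, replacing it, the reason for or time of a switch, or which suction was unclogged.

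On instruments, Section 5 says: "In the control group, the surgeons will utilize standard exposure technique and instruments". For the device arm it adds: "Standard equipment will also be readily available in case the surgeon decides for any reason not to use the device". Section 9 foresees that "the surgeon may not be comfortable using the new instrument, or the device may fail". No section says how to score a clog that ends use of the device, or to which instrument later uncloggings belong.

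**The concern.** The objective concerns blockage of an instrument. The recorded item counts a remedial act on whatever suction is in use. The two agree as long as every blockage is cleared and suctioning goes on with the same instrument. They part when a blockage is dealt with by changing to something else.

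That exit is built into one arm only. A device-arm surgeon with a blocked disposable device has standard suction at hand and may use it. A control surgeon is already on standard equipment and has no trial device to abandon. Two errors can follow in the device arm:

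- the clog that ended device use may not be counted;
- any later unclogging of the standard suction is counted under the device arm.

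The first lowers the device arm's count. The second makes the count describe two instruments. Clogging is one of three stated objectives, and with no follow-up after surgery an event not noted at the time may be impossible to recover.

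**Working it through.** The plan has no clogging figure to reproduce. Its one calculated figure, 36 subjects, concerns exposure time and does not enter here.

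**Inputs from the documents.** Group size is 20 per arm (Section 5: "A total of 40 patients will be randomized, with twenty assigned to each group"). The fallback exists in the device arm only (Section 5).

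**Assumed inputs.** The documents give no clogging rate, abandonment rate or planned clogging test. I assume:

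- true clogging is the same on either suction, Poisson with mean m = 2 to 4 per case;
- each device clog ends device use with probability a = 10%, 25% or 50%;
- that clog is not scored, so at most one is lost per case;
- every later clog of the standard suction is scored;
- the arms are compared by a two-sided t test at 0.05.

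**Step 1: expected loss.** A clog is lost in a case if at least one clog ends device use, which has probability 1 − exp(−a·m). The relative fall in the recorded mean is [1 − exp(−a·m)] / m.

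| a | m = 2 | m = 4 |
|---|---|---|
| 10% | (1 − e^−0.2)/2 = 0.181/2 = 9.1% | (1 − e^−0.4)/4 = 0.330/4 = 8.2% |
| 25% | (1 − e^−0.5)/2 = 0.393/2 = 19.7% | (1 − e^−1)/4 = 0.632/4 = 15.8% |
| 50% | (1 − e^−1)/2 = 0.632/2 = 31.6% | (1 − e^−2)/4 = 0.865/4 = 21.6% |

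**Step 2: false differences.** I simulated 200,000 trials per cell with 20 per arm. Control counts were Poisson(m). Device-arm counts were Poisson(m), less one with probability 1 − (1 − a)^k in a case with k clogs.

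| a | m = 2 | m = 4 |
|---|---|---|
| 0 | 4.9% | 4.9% |
| 10% | 6.9% | 8.0% |
| 25% | 14.6% | 17.3% |
| 50% | 31.7% | 28.0% |

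At a = 25% and 50% nearly all of these false differences favour the device.

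**Step 3: ceiling.** If every first clog ended device use (a = 1), the fall would be (1 − e^−2)/2 = 43% at m = 2 and (1 − e^−4)/4 = 24.5% at m = 4. Abandonment alone cannot remove more than this.

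**Step 4: a device that truly clogs more.** Suppose the device clogs r times as often as standard suction. While it is in use, clogs are scored at (1 − a)·r times the control rate; after a switch they are scored at the control rate. The recorded mean falls below control only if (1 − a)·r < 1, that is a > 1 − 1/r. For r = 1.5 this needs a > 1/3.

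At a = 50% and r = 1.5, the mean fraction of the exposure spent on the device is (1 − e^−1.5)/1.5 = 0.518 for m = 2. The recorded mean is 0.5 × 3 × 0.518 + 2 × 0.482 = 1.74, against 2.00 in control.

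**The case against.** **The wording may already cover the missed clog.** Staff could read the item as counting each time the need to unclog arose, including a clog that was never cleared. This stands: the event can be missed, but it is not certain to be. No rule settles it, so the score depends on who fills in the form.

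**Swapping devices.** A reader might infer that taking a second device is another unscored exit peculiar to the device arm. The documents do not show this. Section 13 says "Ludwig Medical Corporation will provide 40 devices free of charge for the study", which is 40/20 = 2 per planned device-arm patient. It does not say whether the second is a spare or is meant for the other side of the exposure, and Section 22 speaks of one device being brought for each case. A blocked standard suction tip could also be changed without being scored. Only abandonment is clearly specific to the device arm.

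**Size.** A reader might suppose that any share of device-arm clogs can vanish. Removing half of them outright would give false differences in 72% to 95% of trials. Abandonment happens at most once per case, and Step 3 shows that a loss of 50% cannot be reached at either assumed mean.

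**Direction.** A reader might infer that a device discarded early would look clearly better than standard suction. If it is discarded early, nearly all of the exposure is on standard suction and those clogs are counted, so the total resembles control less at most one event. Step 4 shows that a worse device can record fewer clogs, but only if a large share of its clogs end its use.

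**Crediting fallback clogs to the device arm.** As a comparison by assigned group this is legitimate, and the fallback clause may also cover a surgeon who never starts with the device. The total by assigned group should be kept. It does not, however, measure clogging of the device itself.

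**Priority.** Clogging is listed third, and the sample size rests on exposure time. That argues for a modest priority. It does not remove the gap.

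**Conclusion.** The point holds in a limited form. The recorded item does not match the objective: it does not identify the instrument, it can miss the clog that ends device use, and it adds clogs of the fallback suction to the device arm. When such clogs are missed, the comparison shifts in the device's favour.

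Under the stated assumptions the recorded device-arm mean falls by about 8-9%, 16-20% or 22-32% when 10%, 25% or 50% of clogs end device use. A false difference then appears in about 7-8%, 15-17% or 28-32% of trials. The clogging means, the abandonment shares, the Poisson model and the t test are all assumed, so these figures show a range of possible size and do not predict it. The documents do not support saying that such clogs always score zero, or that the bias is large. The change should be made because the measure can mislead on a stated objective and the repair is nearly free.

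**What to change.** Replace the clogging item in Section 5 with: *number of suction blockages during exposure, by instrument (device or standard suction), counted however resolved (cleared, tip or device replaced, or changed to other suction)*. Use the same definition in both arms.

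Record the time of any switch away from the device. Without it, a device set aside early shows few blockages simply because it was used briefly. With it, the device's own blockages can be given per minute of use, which supplies the denominator that the objective lacks.

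Report two results: total blockages by assigned group, and the device's own blockages separately.

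The cost is one reworded field and one time entry on the case form. Nothing changes in what the surgeon may do. The device's clogging figure may become less favourable.

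### The stated 36 subjects (18 per group) cannot be reproduced from the stated inputs; a two-sided test with SD 15 minutes in both groups needs 42 (t test) or 40 (normal approximation)

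*Combined protocol and SAP*

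**What the plan says.** The sample-size justification is a single paragraph under 6) Data Management. It opens: "Power analyses has determined that 36 subjects (2 groups of 18) would be sufficient to demonstrate a significant effect". It then lists what it calls the parameters and assumptions of the analysis:

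- for the control group, "an average exposure time with typical instruments of 30 (± 15) minutes";
- for the expected effect, "a 45% reduction in exposure time previously demonstrated in a previous small study with the new device";
- for allocation, a ratio of 1:1;
- for the error rates, "an alpha value of 0.05 for significance, and power value of 80" per cent.

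It concludes: "Our proposed study size of 40 subjects will therefore confer statistical power". Section 5) Procedures Involved gives the same planned size: "A total of 40 patients will be randomized, with twenty assigned to each group".

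The documents do not name the test, say whether alpha is one- or two-sided, give an SD for the device group, or label ± 15 as an SD. No dropout allowance is given, although 8) Withdrawal of Subjects foresees losses: "Subjects will be withdrawn from the study if their planned surgical procedure is cancelled or changed in such a way" that the inclusion criteria are no longer met.

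**The concern.** The list is presented as the basis of the calculation, so a reader should be able to get from it to 36. With the usual defaults (two-sided alpha, equal SDs) the answer is larger than 36.

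The protocol then argues from 36 to 40, as though 36 were enough and four subjects were spare. If 36 is too low, that reserve does not exist. A team relying on it could regard the loss of four subjects as harmless when it would leave power at about 75% to 77%.

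**Working it through.** **Inputs from the power paragraph.** Control mean 30 minutes; ± 15 read as an SD; 45% reduction; 1:1; alpha 0.05; power 80%.

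**Assumptions added, because the documents are silent.** Two-sided test; SD 15 minutes in the device group as well.

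**Effect.** Difference = 0.45 × 30 = 13.5 minutes (30 to 16.5). Standardized difference d = 13.5 / 15 = 0.90.

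**Attempt to reproduce 36.**

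- Normal approximation: n per group = 2(1.960 + 0.842)² / 0.90² = 2 × 7.849 / 0.81 = 19.38, so 20 per group, **40 in total**.
- Two-sample t test (noncentral t): 20 per group gives 79.2% and 21 per group gives 81.2%, so 21 per group, **42 in total**.

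Neither gives 36.

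**Power at relevant sizes (two-sided, SD 15 in both groups).** By normal approximation with n per group, power = Φ(0.90 × √(n/2) − 1.960). At n = 18 this is Φ(2.700 − 1.960) = Φ(0.740) = 77.0%.

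| Group sizes | t test | Normal |
|---|---|---|
| 18 + 18 | 74.6% | 77.0% |
| 19 + 19 | 77.0% | 79.2% |
| 20 + 19 | 78.1% | 80.2% |
| 20 + 20 (planned) | 79.2% | 81.2% |
| 21 + 21 | 81.2% | 83.1% |

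**Other readings of the same inputs.**

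| Reading | Required total | Power at 18 + 18 (t) |
|---|---|---|
| One-sided 0.05, SD 15 in both groups: 2(1.645 + 0.842)² / 0.81 = 15.27 | 32 (normal and t) | 84.2% |
| Two-sided, device SD scaled to its mean, 0.55 × 15 = 8.25: (15² + 8.25²) × 7.849 / 13.5² = 12.62 | 26 (normal), 28 (t) | 90.1% |
| One-sided, device SD 8.25 | 20 (normal), 22 (t) | not needed |
| Two-sided on the log scale, constant coefficient of variation | 20 (normal), 22 (t) | not needed |

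None of these gives 36.

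**What would give 36.** Three routes were found, and each needs an input the protocol does not state.

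- *A device-group SD a little below 15.* By normal approximation, 18 per group gives exactly 80% power when the SD is √(18 × 13.5² / 7.849 − 15²) = 13.9 minutes. By t test the break-even SD is 13.0 minutes. At or below these values 18 per group is sufficient.
- *A 47% reduction.* The difference is then 14.1 minutes, and 2 × 7.849 × (15 / 14.1)² = 17.77, so 18 per group by normal approximation.
- *A one-sided rank test.* With an efficiency adjustment of 0.864, 15.27 / 0.864 = 17.67, so 18 per group.

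**The case against.** The strongest reply is that this is incomplete reporting, not a demonstrated wrong sum. With the test, the sidedness and one SD unstated, the inputs do not fix a single sample size. The readings above run from 20 to 42 in total, and 36 lies inside that range. A device-group SD near 13 minutes is plausible when the mean is expected to fall from 30 to 16.5, and it could have come from the small study that supplied the 45%. That point stands: 36 has not been shown to be wrong under every choice, and the statement that other readings miss it applies only to those tried. It does not rescue the text, because the paragraph offers its list as the basis for 36 and the list does not lead there.

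The second reply is that the trial enrols 40. By normal approximation 40 is exactly the requirement, and by t test the shortfall is 0.8 points. At 20 per group the t test reaches 80% for a 45.5% reduction instead of 45%, which is within the rounding of the planning figures. This also stands, and it keeps the matter modest.

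The third reply is that losses should be few: the outcome is measured during surgery and no follow-up is required. That is fair. Section 8 gives no withdrawal rate and does not say whether withdrawn subjects are replaced, so any erosion is conditional, at about one percentage point of power per subject lost.

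**Conclusion.** The concern holds. The figure of 36 does not follow from what is written. Under a two-sided test with SD 15 minutes in both groups, which are assumptions because the protocol states neither, it is six subjects short by t test and four short by normal approximation, with power of 74.6% or 77.0% against the stated 80%.

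Under a one-sided test, or with a device-group SD of no more than about 13 minutes (two-sided t test), 18 per group would suffice. The protocol does not say that either applies.

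On the conventional reading, the planned 40 are just below 80% by t test before any loss. By normal approximation they are just above it: one withdrawal leaves 80.2%, and one from each group leaves 79.2%. The four-subject reserve implied by the argument from 36 to 40 is therefore absent. The paragraph should be corrected, but the design does not depend on it.

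**What to change.** Rewrite the power paragraph to name the test, the sidedness and the SD assumed in each group, and replace the claim that 36 is enough with the number those inputs yield. If a two-sided t test with a common SD is intended, suitable wording is:

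> Assuming a two-sided t test at alpha 0.05 and an SD of 15 minutes in both groups, 42 subjects (21 per group) are needed for 80% power to detect a 45% reduction in exposure time. The planned 40 give 79% power; 36 evaluable subjects would give 75%.

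If a different test, a one-sided alpha or a smaller device-group SD was used, state it with its source and give the figure it produces.

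The cost is one reworded paragraph. Enrolment can remain at 40, provided that under the two-sided, common-SD reading the protocol reports about 79% power by t test and claims no margin over 36.

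### Must the Section 5 data list be extended because it names no field for complications, device failure other than clogging, or device use?

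*Combined protocol and SAP*

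**What the plan says.** Section 5 (Procedures Involved) holds the only itemised list of data. It names age, gender, BMI, spinal levels, overall operative time and exposure time, and ends with "blood loss during the exposure, and number of times the suction had to be unclogged". Earlier the same section says, in general terms, "Operative data will be collected". It also provides for the device not being used: "Standard equipment will also be readily available in case the surgeon decides for any reason not to use the device".

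Section 7 (Provisions to Monitor the Data to Ensure the Safety of Subjects) adds no variable and refers back: "The data collected and planned analyses are described above". It then says that data are gathered before, during and after the operation and looked at by study staff. Responsibility is assigned: "The PI will be responsible for data and safety monitoring". The suspension rule reads "The trial will be suspended if a breach of security is observed, or harm is demonstrated to subjects". For data security, a reporting route is written out: "Any suspected or observed breach in data security will be reported to the PI and IRB". No matching sentence covers complications or device failure.

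Section 9 (Risks to Subjects) lists surgeon discomfort with the instrument, device failure leading to delay, and risks not yet known. Section 17 adds general wording on collecting whatever the study needs and on drawing information from the medical records.

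**The concern.** The protocol foresees three kinds of event (harm, device failure and non-use) and has a suspension rule that turns on the first. A reader who goes from that rule to the data list finds no item that would record any of the three directly. Only the clog count comes close, and it covers one type of malfunction.

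Two things seem to be at stake. The first is safety monitoring: if complications are not prompted for in the same way in both arms, the PI's review could depend on what people happen to mention. The second is interpretation. If exposure time does not differ between arms, the listed data alone cannot show whether the device failed to help or was put down in favour of standard instruments. Likewise, a long exposure time in the device arm could reflect a broken device, an unfamiliar one or a hard case.

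**Working it through.** **1. Count of the list.** There are four descriptors (age, gender, BMI, spinal levels) and four operative measures (overall operative time, exposure time, exposure blood loss, clog count), so 4 + 4 = 8 items. Items naming a complication: 0. Device failure other than clogging: 0. Device use: 0. The factual core of the concern is right.

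**2. Objectives against the list.** Section 2 gives three objectives.

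| Objective (Section 2) | Listed measure (Section 5) |
|---|---|
| Operative time and efficiency of exposure | Overall operative time, exposure time |
| Blood loss during exposure | Exposure blood loss |
| "Rate of clogging of suction device" | Number of uncloggings |

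All three are covered. Nothing that the trial sets out to estimate depends on a missing item.

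**3. Foreseen events against the list.**

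- *Device failure.* The only consequence the protocol states is delay in exposure and so possibly longer surgery. Both times are recorded. The cause of a delay is not.
- *Harm.* Blood loss is recorded. Other complications have no named item and fall under the general collection and staff review in Section 7, with the PI responsible.
- *Non-use.* No listed item shows it. This is the most substantial of the three gaps.

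**4. What non-use would do, and what a field would change.** Inputs from the power paragraph at the end of Section 6: control mean 30 minutes, ± 15 read as the SD, 45% reduction, alpha 0.05 taken as two-sided (the plan does not say), power 80%. The planned size is 20 per group.

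Effect: 0.45 × 30 = 13.5 minutes.

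The plan's own figure first. By the normal approximation, n per group = 2 × (1.960 + 0.842)² × 15² / 13.5² = 2 × 7.849 × 225 / 182.25 = 19.4, so 20 per group and 40 in total. The stated 36 (18 per group) is not reproduced; 18 per group gives 77.0% power. The planned 40 agrees with the formula. That mismatch is a separate matter and does not bear on this point.

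Now let a share q of the device arm not use the device and gain nothing, with the SD still 15. Standard error = 15 × √(2/20) = 4.743. Power = Φ(13.5 × (1 − q) / 4.743 − 1.960).

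| Assumed q | Effect (min) | Power |
|---|---|---|
| 0% | 13.50 | 81.2% |
| 10% | 12.15 | 72.6% |
| 20% | 10.80 | 62.4% |
| 30% | 9.45 | 51.3% |

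These q values are assumptions; the documents give none. The formula contains no term for whether non-use is recorded, so power is the same with or without the field. The field would help to explain a null result. It would not prevent one, and it would not alter the estimate by assigned arm.

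**5. What a complication table by arm would show.** With no event among 20 patients, the exact two-sided 95% upper limit is 1 − 0.025^(1/20) = 0.168, about 17%. With so few patients, complications are useful for reviewing individual cases, not for comparing arms.

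**The case for a change.** The strongest case for a change is that the remedy costs almost nothing and that the operation is the main chance to record these facts prospectively, since the protocol requires no postoperative follow-up. The general statements name no field, so they do not guarantee that the same things are written down in both arms. The protocol expressly allows non-use for any reason, and at 40 patients there is little spare power, so knowing how often the device was put aside would help any reader of the results. There is also an imbalance in Section 7: a security breach has a written reporting route and harm does not.

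Part of this stands. Recording device use, with the reason for any non-use, would be good practice and would make the results easier to read. But the Section 5 list is not said to be exhaustive, and no case report form is among the documents, so one cannot conclude that these facts will go unrecorded. The imbalance in reporting routes is a difference in wording more than in substance, because the person responsible for safety is named and can act on any harm that becomes known. To infer that safety review would be ad hoc is to pass over the sentence in Section 7 on perioperative collection and staff review.

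**Conclusion.** No change to the plan is needed. The list does omit all three items, but this is missing detail that study staff and analysts can fill sensibly, for example on the operative data form. Following the plan as written gives no wrong result: every objective has its measure, and the comparison by assigned arm is unaffected. Only the device-use gap has real weight for interpretation, and its effect cannot be sized from the documents. The fall in power from 81.2% to 51.3% over 0% to 30% non-use is an illustration. It assumes ± 15 is an SD, a two-sided test and no benefit in non-users, and it would occur whether or not use was recorded.

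The conclusion rests on reading the general collection statements in Sections 5, 7 and 17 as allowing such items to be recorded, and on the PI carrying out the monitoring that Section 7 assigns. A descriptive note of device use and any complications would be welcome in the trial report, but the plan need not be amended to permit it.
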